3.3.4. Analysis Plan

Table 1. Overview of Analysis Plan

Specific Aim	Analytic Goal	Primary Outcomes (1° outcome underlined)	Secondary Analyses	Analytic Strategy
Aim 1	Evaluate PredicTB Effectiveness	Differences in proportions (pre-post): Treatment initiation (1a) Mortality (1b) Loss to follow-up (1b) Difference in differences (study – comparison) (1c)	Adjustment for age, sex, HIV status, treatment history Regression discontinuity	Mixed-effects log-binomial models (clinic as random effect) Parametric regression discontinuity analysis Difference-in-difference ("product term") model
Aim 2	Evaluate PredicTB Implementation	Reach (2a): % same-day empiric treatment Adoption (2b): % providers using PredicTB Implementation (2c): % of encounters using PredicTB as indicated Maintenance (2d): chg in effectiveness over time	Validation with patient surveys Sensitivity/specificity of empiric tx decisions Association with patient level characteristics	Binomial distribution & confidence intervals w/ clustering by clinic Mixed-effects log-binomial models
Aim 3	Estimate PredicTB Impact & Cost-Effectiveness	Projected reduction in 5-year TB mortality (3a) Incremental cost per DALY averted (3b)	Probabilistic sensitivity analyses Uncertainty analyses Unit cost estimation	Markov state-transition model Cost-effectiveness analysis

Aim 1. Evaluate the effectiveness of the PredicTB clinical risk score on clinical outcomes. Our primary analysis will estimate the absolute difference in the proportion of patients with microbiologically confirmed TB (Xpert or smear; study-driven culture results will be excluded) who are initiated on anti-TB treatment within 7 days of submitting an initial sputum specimen for TB diagnosis, comparing the post-initiation period to the pre-initiation period (dark minus light blue in Figure 2). We will estimate this quantity using a multilevel log-binomial

model, with random-effect terms corresponding to each of the four study clinics. We will perform similar analyses for the proportion of patients with TB who complete treatment and die from any cause (Aim 1b).

This analysis is subject to bias resulting from both secular trends and non-intervention-related effects. We will therefore also perform a difference-in-differences analysis, comparing pre-post effects in the study clinics to those observed in the comparison (non-PredicTB) clinics (Aim 1c). We have not made this our primary analysis because the comparison clinics are smaller (thereby reducing power) and not randomly allocated – for example, staff in these clinics may be less motivated to change behavior. We will also perform a parametric regression discontinuity analysis to estimate the causal effect of implementing the PredicTB risk score (with the discontinuity occurring at the time of implementation). This analysis, however, has less statistical power, and the shape of the effectiveness curve over time in the post-implementation period may reflect important effects (i.e., we are interested not only in the immediate effect of the intervention but also its maintenance over time).

Sample size considerations. Based on patient volumes in 2019, we anticipate a sample size of 1100 patients with confirmed TB: 550 pre-intervention and 550 post-intervention. Using data from our STOMP-TB study,¹³ we expect that 55% of patients will initiate treatment within 7 days in the pre-intervention period. Assuming a design effect of 1.67 due to clustering by clinic, we will have 80% power to detect a difference if treatment initiation increases to 66% in the post-intervention phase and 97% power if treatment initiation increases to 70% (Figure 3).

[figure not shown]

Figure 3. Study power

Aim 2. Evaluate the implementation of the PredicTB clinical risk score. Using the RE-AIM framework^{64,65} as a guide, we will evaluate the implementation of PredicTB according to its reach (proportion of symptomatic patients initiating same-day empiric treatment, Aim 2a), effectiveness (Aim 1), adoption (proportion of providers managing TB in study clinics who use the PredicTB score, Aim 2b), implementation (proportion of eligible patient encounters in which PredicTB is used as indicated), and maintenance (change in effectiveness between month 7 and 18). We will estimate each of these quantities using data from treatment registers and completed PredicTB score sheets and will validate these estimates on the subset of patients who present to treatment during our quarterly site visits. All analyses will include random effect terms to account for clustering of implementation effects at the clinic level.

Aim 3. Project the long-term impact and cost-effectiveness of PredicTB implementation. Based on our experience of estimating the clinical impact of TB treatment regimens^{66,67} and diagnostic tests^{68,69}, we will construct a Markov model of long-term patient outcomes, informed by data from this study. This model will use estimates from the scientific literature to incorporate probabilities of TB mortality, repeat diagnostic attempts, and effectiveness of partial TB treatment. Our primary impact outcome will be the projected reduction in five-year TB mortality effected by PredicTB implementation. We will expand this model to incorporate estimates of costs (which we will empirically measure during the study, using study tools developed by our team for this purpose^{69,70}). We will follow standard guidance for economic evaluation, including inflation using Uganda's GDP deflator, conversion to a common currency and year (2021 US dollars), discounting of all future costs and effectiveness, and measurement of costs as economic (opportunity) costs.^{71,72} We will perform a probabilistic sensitivity analysis (using beta distributions for parameters with defined upper and lower bounds and gamma distributions for those bounded at zero to infinity) to generate 95% uncertainty ranges. We will construct cost-effectiveness acceptability curves, using \$500 per DALY as a conservative cost-effectiveness threshold^{73,74} but also considering revealed thresholds for competing interventions.

3.3.5. Potential Challenges, Alternative Solutions, and Next Steps.

Our biggest challenges include potential reductions in patient volume (e.g., COVID-related) and the possibility that PredicTB will not improve TB treatment initiation (e.g., if uptake is low). If patient volumes are reduced, given the low resource requirement for record abstraction, we will space out our site visits and request a no-cost extension to increase our sample size. If PredicTB does not improve outcomes, this will be an important finding – and the present study will enable us to understand why this occurred, while averting the expense of a major clinical trial. If successful, however, this study will provide preliminary data and justification for such a trial – a trial with the potential to effect a major change in clinical practice and improve meaningful outcomes for patients with TB in the most resource-constrained settings. Given the tremendous burden of morbidity, mortality, and transmission risk borne by these patients – coupled with the short timelines of global End TB targets – the need for easy-to-use interventions that improve TB management could not be more urgent.

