3.3 Research Design and Methods

3.3.1. Study setting and design

We will conduct this study in four primary health clinics in peri-urban Uganda (with four additional clinics serving as a comparison). Uganda is one of 30 high TB burden countries recognized by World Health Organization (WHO), with an estimated 2018 TB incidence of 200 per 100,000; 41% of those cases were co-infected with HIV.¹ Like many countries in East Africa, Uganda is among the world's poorest countries with an estimated per-capita gross domestic product (GDP) of \$777 2019;⁶⁰ the drivers of its TB epidemic are multifaceted,⁶¹ and there is relatively little drug resistance. Most TB in Uganda is diagnosed in public sector health facilities, and despite national guidelines promoting the use of Xpert, sputum smear microscopy remains the primary diagnostic assay used.⁵⁴ Diagnostic and treatment delays are common,⁶² resulting in a large number of untreated prevalent cases; the 2014-15 Ugandan National TB Prevalence Survey⁶³ estimated the prevalence of bacteriologically confirmed TB at 401 per 100,000 adults. These conditions are typical of sub-Saharan Africa (outside of South Africa); thus, findings from our study are likely to be broadly relevant.

We have selected four study clinics based on the following criteria: (a) within 150km of the capital city, Kampala; (b) no access to same-day Xpert testing (a criterion that effectively excludes clinics in Kampala proper); (c) high-quality TB record-keeping; (d) at least 100 bacteriologically confirmed TB cases diagnosed in 2019 (which effectively excludes private-sector clinics); and (e) clinic in-charge willing to have clinic staff trained in use of the PredicTB tool. We have also selected four comparison clinics that are similar in location and patient population to the four primary study clinics, but for which the latter two criteria were relaxed.

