3.3.3. Study procedures

[figure not shown]
In the pre-implementation phase

(month -6 to month 6), study and comparison clinics (selected as already having high-quality TB records) will continue to maintain standard TB registers. These registers include all individuals who have sputum sent for TB diagnosis with sputum smear and/or Xpert ("presumptive register") and all individuals who are started on TB treatment ("treatment register"). We will abstract key data from these registers, including age, sex, prior TB treatment, HIV status, diagnostic result, and treatment outcome. During month 1 of the study, we will initiate a retrospective abstraction of all registers from month -6. We will also begin prospective abstraction of registers by having routine clinic staff take photos of registers and securely transfer them to our study team, who will upload these into a REDCap database. Staff from the XPEL-TB trial⁴⁴ have experience in these procedures (including the development of a pre-existing database for this purpose), so we will be able to initiate this abstraction rapidly and seamlessly.

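### The primary before-after estimate leaves out age, sex, HIV status and prior TB treatment, although the plan abstracts them and already adjusts for them as a secondary analysis

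*Combined protocol and SAP*

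**What the plan says.** Section 3.3.4 (Aim 1) defines the primary quantity as the absolute difference, post minus pre, in the proportion of patients with Xpert- or smear-confirmed TB who start treatment within 7 days of giving sputum. It is to come from a multilevel log-binomial "model, with random-effect terms corresponding to each of the four study clinics". No patient characteristic is named in that model.

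Table 1 of the same section puts "Adjustment for age, sex, HIV status, treatment history" in the Secondary Analyses column for Aim 1. Section 3.3.3 shows where the variables come from: "We will abstract key data from these registers, including age, sex, prior TB treatment, HIV status, diagnostic result, and treatment outcome".

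The plan is open about the weakness of the primary comparison: "This analysis is subject to bias resulting from both secular trends and non-intervention-related effects". It responds with a difference-in-differences analysis against four comparison clinics and a regression discontinuity analysis. It explains why neither is primary; of the first it says "We have not made this our primary analysis because the comparison clinics are smaller (thereby reducing power) and not randomly allocated". It gives no such explanation for keeping the patient covariates out of the primary model.

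**The concern.** In a before-after comparison, nothing in the design makes the patients of the second year resemble those of the first. If the share of a patient group that starts treatment faster or slower changes between the years, the unadjusted difference counts that change as an effect of PredicTB.

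The documents give some reason to take this seriously. Section 3.3.5 names falling patient volumes, for example from COVID, as a leading challenge; that the type of patient attending might change along with the volume is my inference. Sex, age and self-reported HIV status are inputs to the PredicTB score (section 3.2.1), so after implementation they are meant to influence who is treated the same day. They are plausible predictors of the outcome.

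The headline estimate is meant to inform whether a larger cluster-randomised trial is justified. A distortion of a few points in either direction could tilt that decision, and part of it can be removed with data the study already plans to collect.

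**Working it through.** **Inputs from section 3.3.4 (sample size considerations):** 550 patients per period; 55% pre-period initiation; design effect 1.67; 80% power for 66% and 97% power for 70% in the post period. Alpha is not stated; I assume 0.05 two-sided.

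**Step 1: reproduce the plan's power.** Effective n per period = 550 / 1.67 = 329.3. For 55% against 66%:
- SE under the alternative = √[(0.55×0.45 + 0.66×0.34) / 329.3] = 0.0379.
- SE under the null, with pooled proportion 0.605 = √[2×0.605×0.395 / 329.3] = 0.0381.
- Power without continuity correction = Φ[(0.11 − 1.96×0.0381) / 0.0379] = 82.5%.
- Power with continuity correction (subtract 1/329.3 from the difference) = 80.3%.

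For 55% against 70% the same formulas give 97.9% and 97.5%. The corrected version matches the stated 80% and 97%, so the effective n is a fair basis for what follows.

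**Step 2: precision.** 95% half-width at 55% and 66% = 1.96 × 0.0379 = 7.4 points.

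**Step 3: spurious difference from case-mix drift.** For one binary covariate whose gap in 7-day initiation is the same in both periods:

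bias = (change in the covariate's share) × (gap in 7-day initiation)

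The documents give neither factor, so both are assumed:

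| Shift in share | Gap 10 points | Gap 20 points |
|---|---|---|
| 5 points | 0.5 points | 1.0 points |
| 10 points | 1.0 points | 2.0 points |

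For scale, section 3.3.1 gives a national HIV share of 41% among TB cases. A move from 41% to 51% with a gap of 10 to 20 points would give 1 to 2 points, which is 9% to 18% of the 11-point target (1/11 and 2/11).

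**Step 4: consequence for the test.** With no true effect and a spurious difference b, SE = √[(0.55×0.45 + (0.55+b)(0.45−b)) / 329.3], and the two-sided rejection probability is 1 − Φ(1.96 − b/SE) + Φ(−1.96 − b/SE).
- b = 0.5 points: 5.2%.
- b = 1 point: 5.8%.
- b = 2 points: SE = 0.0387, b/SE = 0.517, so 7.45% + 0.66% = 8.1%.

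Drift the other way costs power. With a true 11 points and 2 points of adverse drift, the observable difference is 9 points, and power by the uncorrected formula falls from 82.5% to 65.3%. With 1 point it falls to 74.6%.

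**Step 5: upper limit of the argument.** For one covariate with a 20-point gap to produce the whole 11 points, its share would have to move by 0.11 / 0.20 = 55 points.

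**The case against.** The strongest reply is that the plan has largely dealt with this. The adjusted analysis is prespecified with the four covariates I would use. The plan admits the bias and adds two further analyses. Difference-in-differences removes drift shared with the comparison clinics, and regression discontinuity addresses gradual drift. All of that stands: the defect is which estimate carries the headline, not a missing adjustment. It does not justify the ordering, because difference-in-differences leaves drift that is specific to the study clinics, and the plan itself describes that analysis as having less power and a non-randomised comparison.

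A second reply is that the bias is small against a half-width of 7.4 points, and that this is a preliminary study. That also stands, and it limits how strongly the point can be put.

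Three stronger readings may tempt a reader, and the documents do not support them:
- *A shift from smear to Xpert could produce a much larger bias.* Section 3.3.1 says that "despite national guidelines promoting the use of Xpert, sputum smear microscopy remains the primary diagnostic assay used", but this describes Uganda at one time, not a changing mix in these clinics. Section 3.3.3 lists the diagnostic result and does not say that the type of test is abstracted. Test choice may also change with the month-7 training given to all eight clinics, so it does not belong in the main adjustment set, and the change proposed here would not remove such a bias.
- *The analysts could pick the adjusted or unadjusted result after seeing both.* Table 1 fixes the order in advance.
- *The covariates are complete for every patient.* Section 3.3.3 says they are abstracted from routine registers and says nothing about completeness.

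**Conclusion.** The concern holds as a matter of which estimate is primary. The headline difference is unadjusted in a non-randomised before-after design, the covariates are to be abstracted, adjustment for them is already planned, and no reason is given for ranking it second. Under the assumed shifts (5 to 10 points) and gaps (10 to 20 points), the avoidable bias is about 0.5 to 2 points in an unknown direction. At the top of that range, two-sided type I error goes from 5% to about 8%, assuming alpha of 0.05 and the plan's own design effect.

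A reader should not infer that case-mix drift could plausibly explain an 11-point improvement, or that adjustment would make the before-after comparison causal. It removes measured drift only. Secular trend, standard-of-care training and performance feedback remain in the estimate. This is a worthwhile, low-cost improvement rather than a fatal flaw.

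**What to change.** In section 3.3.4 and Table 1, make the primary estimate the covariate-standardised absolute risk difference:
- Fit a model for 7-day initiation with period, clinic, age, sex, HIV status and prior TB treatment. Predict each analysed patient's risk under post and under pre, average each set, and subtract. This also settles how an absolute difference is obtained, since a log-binomial model by itself returns a ratio.
- State how clinic enters the model, and name an interval method for the standardised difference that accounts for clustering with only four clinics.
- Report the unadjusted difference beside it, and tabulate case mix by period so that readers can see any drift.
- Where the registers record the confirming test, use it only in a sensitivity analysis stratified by smear or Xpert.
- Keep the difference-in-differences analysis, which addresses what covariate adjustment cannot.

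The cost is SAP wording, slightly more programming and a stated rule for missing covariates, with no new data collection. That rule needs care. An unknown category for HIV status is one option, but if completeness differs between the periods it could itself distort the adjusted estimate, so missingness should be tabulated by period as well. If the sponsor prefers to keep the unadjusted estimate primary, the plan should give the reason.

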3.3.2. Study overview

The overall goals of this proposal are to estimate the effectiveness of the PredicTB clinical risk score in improving clinical outcomes for patients with pulmonary TB and to generate pragmatic data regarding the implementation of this score in highly resource-constrained primary health clinics. If successful, this study will provide an evidence base to justify the design and conduct of a larger cluster-randomized trial. This study will be conducted as a type 2 hybrid effectiveness-implementation evaluation. Our primary effectiveness outcome will be the difference in the proportion of adults with bacteriologically confirmed pulmonary TB who initiate treatment within 7 days of submitting sputum for TB diagnosis, comparing the 12 months before implementing

the PredicTB score to the 12 months after implementation. Secondary analyses will assess for the potential that measured differences reflect improved general practice and/or secular trends. Our primary implementation outcome will be the proportion of patients in the study clinics in whom the PredicTB score is used as indicated. Our study will consist of four phases (Figure 2): pre-implementation, implementation, post-implementation, and end phase. We will adopt a highly pragmatic study design in which we minimize involvement of study staff in the clinics under evaluation, with the exception of the intervention itself.

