In the **implementation phase** (month 7), we will train clinic staff in all eight clinics (study clinics and comparison clinics) on the Ugandan standard of care for diagnosis and treatment of TB. In addition, in the four study clinics, we will provide training on the PredicTB score. This training will include the following elements: (a) background on the PredicTB score and its aim of informing empiric treatment decisions for adult pulmonary TB; (b) provision of materials (paper score sheets and laminated instruction sheets) to enable clinicians to use the PredicTB score; (c) reinforcement that all treatment decisions are ultimately at the discretion of the treating physician; (d) reinforcement that PredicTB is not meant to be a replacement for microbiological testing – that sputum should be sent for microbiological testing in all patients presenting with symptoms of TB, and that any patient with a positive microbiological test should be treated for TB. Prior to this training, we will speak with the head (in-charge) physician at each of the four study clinics to describe the PredicTB score and elicit the physician's recommendations as to the percentage of TB tests that are positive in the clinic (i.e., columns in Figure 1) and the score that should be encouraged as a threshold for same-day empiric treatment initiation. Importantly, this threshold may vary from one clinic to another; our analyses will not explicitly incorporate this threshold as a covariate, but we will explore clinic-by-clinic variation by way of informing any future clinical trial. Furthermore, we will seek the in-charge physician's advice regarding an alternative approach in which patients with high (e.g., >40%) risk could be scheduled for a full treatment course, whereas those with intermediate (e.g., 10-40%) risk could be prescribed a provisional (e.g., 14-day) course, which could be discontinued if microbiological testing for TB was negative and the clinical course [e.g., full resolution in 1-2 days or continued worsening of symptoms despite TB therapy] were inconsistent with a diagnosis of TB. Training in the use of the PredicTB risk score in each clinic will therefore follow the recommendations of each clinic's in-charge physician and will only augment (not supplant) the Ugandan standard of care for TB management. We will re-evaluate these recommendations every three months during site visits (see below) and update training as needed.

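### The primary model and the power calculation assume different variances for the same pre-post difference, so either the stated power or the primary interval is wrong

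*Combined protocol and SAP*

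**What the plan says.** Section 3.3.4, Aim 1, defines the target: "Our primary analysis will estimate the absolute difference in the proportion of patients with microbiologically confirmed TB" treated within 7 days, after implementation versus before. The method follows: "We will estimate this quantity using a multilevel log-binomial" model, "with random-effect terms corresponding to each of the four study clinics". Table 1 has the same entry for Aim 1: "Mixed-effects log-binomial models (clinic as random effect". For this analysis neither place names a clinic-by-period term, a random period slope, a robust variance or a small-sample reference distribution.

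The sample size paragraph of the same section expects 550 confirmed cases per period and 55% treated within 7 days beforehand. It continues: "Assuming a design effect of 1.67 due to clustering by clinic, we will have 80% power to detect a difference" if the proportion rises to 66%, and gives 97% for a rise to 70%. It states no intracluster correlation, and does not say whether the clustering is a stable clinic level or change that differs between clinics.

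**The concern.** A design effect and a random clinic intercept are both ways of allowing for clinics, so the two statements look consistent. For a pre-post contrast within the same clinics they are not. An intercept describes how clinics differ in level, and that difference is common to both periods. It does not add to the variance of the change. The design effect, as used in the power statement, does add to it.

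The interval and test of the primary outcome are at stake, together with the power statement. Section 3.3.2 gives the result a definite use: "If successful, this study will provide an evidence base to justify the design and conduct of a larger cluster-randomized trial". A reader should be able to tell whether the interval allows for clinics changing by different amounts.

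**Working it through.** **Inputs.** From section 3.3.4: 550 patients per period, 55% before, 66% or 70% after, design effect 1.67. From section 3.3.1: four study clinics, hence 550/4 = 137.5 patients per clinic and period if sizes are equal (assumed). Two-sided 5% is also assumed, since the plan states no alpha.

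**Step 1: reproduce the stated power.** Effective size per period is 550/1.67 = 329.3. At 66%:
- Null SE: √(2 × 0.605 × 0.395/329.3) = 0.0381.
- Alternative SE: √[(0.55 × 0.45 + 0.66 × 0.34)/329.3] = 0.0379.
- Continuity correction: 1/329.3 = 0.0030.
- Power: Φ[(0.11 − 0.0030 − 1.96 × 0.0381)/0.0379] = 80.3%.

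The same steps at 70% give 97.5%. Both agree with the plan. Without the continuity correction the figures are 82.5% and 97.9%. Without the design effect they are 96.3% and 99.9%. The stated power therefore multiplies the variance of the pre-post difference by 1.67.

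**Step 2: what the model reports.** With log p = α + β × period + u for a clinic with intercept u, the within-clinic log ratio of after to before is β, and u cancels. What remains is roughly the binomial variance: (0.2475 + 0.2244)/550 = 0.000858, SE 0.0293. The power calculation uses 0.0293 × √1.67 = 0.0379. With a normal reference the 95% half-widths are 1.96 × 0.0293 = 5.7 points and 1.96 × 0.0379 = 7.4 points.

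**Step 3: stable clinic differences.** If all of the 1.67 is stable level, it corresponds to an intracluster correlation of 0.67/136.5 = 0.0049 and cancels from the contrast. In 3,000 simulated trials per setting, with the random-intercept log-binomial model fitted by maximum likelihood, the 95% interval missed 4.9% of the time under no effect. Power at 66% was 96%.

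**Step 4: clinic-specific change.** Let s be the share of the excess variance that is clinic-by-period. The variance of the difference is then inflated by D = 1 + 0.67s, and an interval that ignores D misses with probability 2[1 − Φ(1.96/√D)]. The simulated column is for a log-binomial fit with clinic terms, standardised over clinics, under no effect (8,000 runs per setting).

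| s | D | formula | simulated |
|---|---|---|---|
| 0% | 1.00 | 5.0% | 5.3% |
| 25% | 1.1675 | 7.0% | 7.6% |
| 50% | 1.335 | 9.0% | 9.3% |
| 100% | 1.67 | 12.9% | 12.9% |

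At s = 100% and a true rise of 11 points the simulated figure is 14.3%. The random-intercept model at s = 100% missed 13.3 to 13.9% under no effect and 13.2% at +11 points. These simulations used assumed clinic baselines of 45, 52, 58 and 65%, or assumed between-clinic SDs of 0 to 10 points. With all baselines equal at 55% the rate was 14.2%, so the spread of baselines does not drive it. An s of 100% means clinic proportions shifting between periods with an SD of √(0.67 × 0.2475/137.5) = 3.5 points per clinic and period.

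**Step 5: four clinics.** A clinic-specific period effect with a normal reference still missed 7 to 9% in simulation, because four clinics estimate that variance poorly. A t interval on the four clinic differences (3 df) missed about 5%. Its half-width is 3.182 × 0.0379 = 12.0 points. By the noncentral t distribution its power is 51% at 66% (0.11/0.0379 = 2.91) and 76% at 70% (0.15/0.0373 = 4.02).

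**The case against.** The best defence is that the ordinary source of a design effect for clustering by clinic is stable differences between clinics. On that reading the interval has nominal coverage and the power statement is merely conservative. This is a fair reading and the documents do not exclude it. It still leaves the stated 80% and 97% wrong for the analysis named.

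A reader might go further and infer that the primary interval misses 13 to 14% of the time. The documents do not support that as a flat statement. It is the extreme of a range that starts at 5%, and the plan does not give the share. Two places seem to point to the extreme, but the evidence is weak:
- Section 3.3.3 says "this threshold may vary from one clinic to another; our analyses will not explicitly incorporate this threshold as a covariate". Threshold differences act only after implementation, and they cannot create false positives if the score has no effect. Inflating only the later period by 1.67 gives a design effect of about (1 + 1.67)/2 = 1.34 and a miss rate near 9%. The same sentence also commits to exploring variation between clinics.
- Section 3.3.4 concedes "This analysis is subject to bias resulting from both secular trends and non-intervention-related effects". That concerns bias, not change that differs by clinic. The difference-in-differences and regression discontinuity analyses answer it, but they do not alter the primary standard error.

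The plural wording about random-effect terms, and a sentence under Aim 2 on clinic-level variation in implementation, could be read as allowing clinic-specific effects. Nothing in Aim 1 says so, and Table 1 points to an intercept.

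A reader might also conclude that an observed rise of 6 to 12 points would be significant only by an invalid analysis, or that the planned 11-point rise is out of reach. Both depend on adding the 3-df reference. With 1.67 in the variance and a normal reference, the half-width is 7.4 points, 11 points remains significant, and power is about as stated. The t reference is costly by itself: with no clinic-by-period variation at all, it cut simulated power at 66% from 96% to 69%. Whether to make it primary is a matter on which reasonable statisticians differ, particularly as the four clinics were chosen on purpose.

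**Conclusion.** The mismatch holds under either meaning of the 1.67, and should be fixed before analysis. With stable clinic differences, the interval is sound and the stated 80% power at 66% should be about 96%. With clinic-specific change, the interval is too narrow, with a miss rate between 5% and 13 to 14% depending on a share that the plan does not state. The standard errors in conflict are 2.9 and 3.8 points.

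This rests on reading the model as one random intercept per clinic, equal clinic sizes, two-sided 5%, and the 1.67 applying to the variance of the difference, which is the use that reproduces the stated power. The point estimate is not in question: the absolute difference can be recovered from the log-binomial fit by standardising over clinics.

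**What to change.** State what the 1.67 represents, and use one variance assumption in the Aim 1 analysis and the sample size paragraph. There are two options:

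- **Drop the 1.67.** Restate the power (about 96% at 66% and 99.9% at 70%) and say that the interval assumes a common change in all four clinics.
- **Keep the 1.67.** Add a clinic-by-period random effect, or base the interval on the four clinic-specific differences, and restate the power for that analysis. The price is a wider interval: half-width 7.4 instead of 5.7 points with a normal reference. Because that reference still under-covers somewhat with four clinics, report the four differences with a 3-df t interval at least as a sensitivity analysis, and state its half-width (about 12 points) and power (about 51% and 76%) openly.

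In either case, say that the absolute difference is obtained by standardisation over clinics, and report the four clinic-specific differences. The work is plan wording and minor programming, with no new data.
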